In-depth interviews: Additionally, in-depth interviews (IDIs) will be conducted with a selection of 10 women from each intervention condition (30 IDIs), purposively sampled based on high/low participation rates determined by the end line survey. We will collect data on experiences with *MeSSSSage* and how to improve it.

Technology assessment: Finally, we will collect and analyze the quantitative backend data from the prototype to gain more insight into women's participation in the intervention, including attendance and level of participation

in group interactive educational sessions, use of mobile social support platform (number of posts, frequency, topic), etc. Text data from transcripts of the educational sessions and content of group messaging will be analyzed for content in order to understand primary educational needs and interests for postnatal women.

Group moderator survey and interview: ASHA facilitators moderating the groups will be asked to respond to a short questionnaire after each group session to understand: preparation and delivery time, content, efficiency, acceptability and satisfaction with the group model, perspectives of impact, challenges, and any follow-up/referral necessary.⁴⁰ Regarding facilitation of groups that receive the text-based messaging intervention component only, ASHA facilitators will report on experiences in the prior week. We will conduct monthly semi-structured interviews with each of the ASHA facilitators to understand their preferences for group components, experiences preparing for and conducting the sessions, and their perspectives on mobile provision of education, care, and support.

Measures: The baseline survey content will include sociodemographic characteristics and knowledge about maternal and infant health, self-efficacy, and perceived social norms regarding MCH-related health promoting behaviors. The endline survey will include acceptability questions such as women's satisfaction with and perceptions of *MeSSSSage*, maternal and infant knowledge-, behavior-, and health-related questions including about breastfeeding, complementary food introduction, immunization, family planning uptake, maternal physical and mental health, etc. which have previously been used in this setting (Table 3)⁴.

Table 3: Participant survey measures (Phase 2)

Category	Measures

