Aim 3. Preliminary effectiveness of the MeSSSSage intervention components on six-month MCH outcomes. Using the quantitative survey data, we will statistically evaluate differences by study arm in improvements in women's knowledge, behaviors, and maternal and child health outcomes, compared to the control group (including effect sizes, controlling for relevant socio-demographics as necessary). Figure 1 displays the outcomes that are theoretically related to our intervention targets. Our main *knowledge* outcome will be a composite score representing the proportion of correct answers from a knowledge scale on breastfeeding, newborn and infant care, maternal and infant danger signs, newborn care, and family planning, topics that will be covered within our interactive educational group component. Our main *behavior* outcome will be self-reported exclusive breastfeeding at 6 months. Our main *health related* outcomes will be: (1) completion of early childhood immunization schedule; and (2) postnatal family planning uptake. We will measure women's social support and related mental health status (depression and anxiety) using scales that have been previously validated in similar populations such as the Hopkins Symptom Checklist⁴¹ and the Multidimensional Scale of Perceived Social Support⁴². Finally, women's empowerment will be measured using decision-making and mobility scales.^{43,44}

Sample Size. This pilot development study is not formally powered to detect significant differences in outcomes, but will give insight into directionality of changes. The per group sample size was selected based on feasibility

of recruitment, intervention delivery, and the interpersonal interaction important for a group-focused intervention. The sample is sufficiently large to assess the feasibility and acceptability outcomes through descriptive statistics.

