Feasibility. To evaluate feasibility of the intervention, we will monitor enrollment rates and moderator effort required (e.g. number of staff hours). An enrollment rate of 70% or higher will be considered feasible, as the established standard in intervention literature. Through moderator report we will confirm effort required for preparation, session delivery, and follow-up. We will also capture any technological challenges. This information will inform staffing needs and retention protocols for a subsequent full trial.

Acceptability. To measure acceptability, we will use a client satisfaction questionnaire which will capture self-reported engagement in intervention components and topics, satisfaction with intervention components, likelihood of participating again, likelihood of recommending program, and value on knowledge and social support gained from participation.

Preliminary effectiveness. To measure effectiveness, we will health-related knowledge (maternal and neonatal danger signs, best practices for infant care, and family planning), health-related behaviors (breastfeeding and complementary food introduction practices (breastfeeding initiation, length of exclusive breastfeeding, length of breastfeeding, timing of complementary food introduction), appropriate management of early childhood

illnesses), and health outcomes (Early childhood immunization, postnatal depression and anxiety, postnatal contraceptive adoption.)

Quantitative analyses: With a between-groups design, each participant will participate in only one arm of the trial, thus we will assess quantitative intervention outcomes by factor (voice and text) through fitting a series of the following linear regression model:

$$y_i = \beta_0 + \beta_1 Z_{1i} + \beta_2 Z_{2i} + \beta_3 Z_{1i}Z_{2i} + \varepsilon_i$$

Where y_i is the outcome for the i^{th} participant, β_0 is the coefficient for the intercept (standard of care), β_1 represents the mean difference in factor 1 (voice), β_2 represents the mean difference in factor 2, (text) β_3 represents the interaction between factor 1 and factor 2 (voice + text), Z_{1i} is the indicator variable for factor 1, Z_{2i} is the indicator variable for factor 2, and ε_i is the residual for the i^{th} participant. Due to the modest sample size, significance testing will be deemphasized and we have not included power analyses for this study.

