Text-based, asynchronous, on-demand social support: App-based small group text-based communication. Moderated by health professional. (text)		X	X	
Standard of care: 3 visits in the first 7 days postnatal (facility and home)	X	X	X	X

The following intervention characteristics will be assessed:

Feasibility. To evaluate feasibility of the intervention, we will monitor enrollment rates and moderator effort required (e.g. number of staff hours). An enrollment rate of 70% or higher will be considered feasible, as the established standard in intervention literature. Through moderator report we will confirm effort required for preparation, session delivery, and follow-up. We will also capture any technological challenges. This information will inform staffing needs and retention protocols for a subsequent full trial.

Acceptability. To measure acceptability, we will use a client satisfaction questionnaire which will capture self-reported engagement in intervention components and topics, satisfaction with intervention components, likelihood of participating again, likelihood of recommending program, and value on knowledge and social support gained from participation.

Preliminary effectiveness. To measure effectiveness, we will health-related knowledge (maternal and neonatal danger signs, best practices for infant care, and family planning), health-related behaviors (breastfeeding and complementary food introduction practices (breastfeeding initiation, length of exclusive breastfeeding, length of breastfeeding, timing of complementary food introduction), appropriate management of early childhood

illnesses), and health outcomes (Early childhood immunization, postnatal depression and anxiety, postnatal contraceptive adoption.)

Quantitative analyses: With a between-groups design, each participant will participate in only one arm of the trial, thus we will assess quantitative intervention outcomes by factor (voice and text) through fitting a series of the following linear regression model:

$$y_i = \beta_0 + \beta_1 Z_{1i} + \beta_2 Z_{2i} + \beta_3 Z_{1i}Z_{2i} + \varepsilon_i$$

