Where y_i is the outcome for the i^{th} participant, β_0 is the coefficient for the intercept (standard of care), β_1 represents the mean difference in factor 1 (voice), β_2 represents the mean difference in factor 2, (text) β_3 represents the interaction between factor 1 and factor 2 (voice + text), Z_{1i} is the indicator variable for factor 1, Z_{2i} is the indicator variable for factor 2, and ε_i is the residual for the i^{th} participant. Due to the modest sample size, significance testing will be deemphasized and we have not included power analyses for this study.

Hypotheses for preliminary/exploratory analyses on effectiveness. Exploratory hypotheses will be evaluated as part of the study feasibility assessment process. Means and proportions will be plotted by group over time to enable descriptive evaluation of overall patterns of change across time in the outcomes for the intervention and control groups. For example, we expect that following intervention exposure, relative to control group participants, intervention participants will have improved health-related knowledge, health-related behavior, and health outcomes. We also anticipate that intervention participants receiving both voice and text components will have the highest report of the prior outcomes and reported social support, and we will explore differences in these outcomes and in levels of reported social support between the groups as described above.

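### For the knowledge composite, the effectiveness model does not say whether the outcome is the endline score or the change, and it has no baseline-knowledge term; this costs some precision but causes no bias

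*SAP*

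**What the plan says.** The protocol and the SAP, both under Statistical Design and Power (Quantitative analyses), give the same single regression for effectiveness outcomes. The SAP says "we will assess quantitative intervention outcomes by factor (voice and text) through fitting a series of the following linear regression model", and the protocol introduces the model with "each participant will participate in only one arm of the trial, thus we will assess quantitative intervention outcomes by factor". The terms are an intercept, a voice indicator, a text indicator and their product. The dependent variable is defined only in this way: y "is the outcome for the i^{th} participant".

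The protocol's Analysis section, Aim 3, adds two relevant statements. It says "we will statistically evaluate differences by study arm in improvements in" knowledge, behaviours and health outcomes, which leans towards change. It also allows adjustment, "controlling for relevant socio-demographics as necessary". The main knowledge "outcome will be a composite score representing the proportion of correct answers from a knowledge scale", with no time point attached. The SAP repeats neither the word improvements nor any covariate.

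On measurement, the protocol's Measures paragraph says "The baseline survey content will include sociodemographic characteristics and knowledge about maternal and infant health", and it lists knowledge questions for the endline survey as well. The Hypotheses paragraph, present in both documents, plans to plot means and proportions by group over time.

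**The concern.** Knowledge is the one main outcome with a value before the intervention. Exclusive breastfeeding, immunisation and family planning uptake have none. The written model makes no efficient use of that value under either reading of y. If y is the endline score, baseline knowledge does not enter the regression. If y is the change, baseline is subtracted with a fixed weight of 1 instead of a weight estimated from the data.

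The protocol promises effect sizes (Analysis, Aim 3) and says the pilot will inform a larger trial (Expected outcomes and future directions). Since testing is de-emphasised, interval width is what the reader of the pilot will use. Leaving y open also means that endline or change could be chosen after the data are in, and the two can give intervals of different width.

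**Working it through.** **Inputs from the documents.** 160 women, 40 per arm, four arms (Specific Aims, Aim 2); two groups per condition, eight in all (Recruitment), hence 160/8 = 20 per group. The documents give no SD, power or precision target, so there is no figure of theirs to reproduce.

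**Assumed inputs.** The baseline-endline correlation r, the ratio k of baseline SD to endline SD, and the intraclass correlation (ICC) are not in the documents. A range is shown for each.

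**Formula.** Take the within-arm endline SD as 1. The large-sample 95% half-width for one arm against control is 1.96 × sqrt(2f/n), where
- endline score: f = 1
- change score: f = 1 + k² − 2rk, which is 2(1 − r) when k = 1
- endline adjusted for baseline: f = 1 − r²

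**Ordering.** Endline minus adjusted is r². Change minus adjusted is 1 + k² − 2rk − (1 − r²) = (k − r)². Neither can be negative, so in large samples and without clustering, adjustment is never less precise than either alternative. It ties with endline only at r = 0 and with change only at k = r. For example, at k = r = 0.8 both variances are 0.36.

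**Half-widths, n = 40 per arm, k = 1, no clustering or dropout (SD units):**

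| r | Endline | Change | Adjusted |
|---|---|---|---|
| 0.2 | 0.44 | 0.55 | 0.43 |
| 0.3 | 0.44 | 0.52 | 0.42 |
| 0.5 | 0.44 | 0.44 | 0.38 |
| 0.7 | 0.44 | 0.34 | 0.31 |

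Worked line for r = 0.3: endline 1.96 × sqrt(2/40) = 0.438; change 1.96 × sqrt(2 × 1.4/40) = 0.519; adjusted 1.96 × sqrt(2 × 0.91/40) = 0.418. A simulation of the four-arm model (4,000 runs per r) gave adjusted standard errors of 0.217, 0.196 and 0.160 at r = 0.3, 0.5 and 0.7, against 0.213, 0.194 and 0.160 from the formula.

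**Unequal SDs.** At r = 0.5, the change half-width is 0.40 SD for k = 0.8 (f = 0.84) and 0.50 SD for k = 1.25 (f = 1.3125). The adjusted value stays at 0.38. The variance saved against change is then 1 − 0.75/0.84 = 11% or 1 − 0.75/1.3125 = 43%, compared with 25% at k = 1.

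**Dropout.** With an assumed 20% loss (32 per arm), k = 1 and r = 0.5, the half-widths are 0.49 SD for endline and for change, and 0.42 SD adjusted.

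**Clustering.** Take two groups of 20 per arm, r within group, and baseline not predicting the group effect. The variance of an arm mean is [ICC + (1 − ICC)f/20]/2; for a control arm that never meets as a group it is (1 − ICC)f/40. At r = 0.5 the variance saved against endline is:
- both arms grouped, ICC 0.02: 1 − 0.028375/0.0345 = 17.8%
- both arms grouped, ICC 0.10: 1 − 0.066875/0.0725 = 7.8%
- control not grouped, ICC 0.02: 1 − 0.04675/0.059 = 20.8%
- control not grouped, ICC 0.10: 1 − 0.08375/0.095 = 11.8%

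The saving is therefore about 8-21%. With k = 1 and r = 0.5 it is the same against change, because f = 1 for both. At r = 0.2 the saving against endline is 4% without clustering and 1.2-3.3% with it. Clustered results are given as variance ratios only, because 1.96 is too small a multiplier with two groups per arm.

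**The case against.** The strongest reply is that this is a feasibility pilot. Both documents say it is not powered and that testing will be de-emphasised, no precision target exists, and the gain rests on an r that nobody has stated. At r = 0.3 the half-width moves only from 0.44 to 0.42 SD against endline. This stands, and it limits the weight of the point.

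It can also be said that the equation is a template for a series of models, that Aim 3 already allows covariates, and that improvements read with the plots over time suggests change. This stands in part: the documents lean towards change. But the wording is not tied to y, the SAP does not carry it, and the permitted covariates are socio-demographic.

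Three stronger readings are tempting and are not supported:
- A reader might infer that baseline knowledge would go wholly unused if y is the endline score. It would be absent from the regression, but both documents plan plots over time.
- A reader might infer that a change score is always less precise than adjustment when r is below 1. That needs k to differ from r, and the documents give no SDs.
- A reader might infer that the baseline survey omits family planning knowledge, because the composite covers "newborn and infant care, maternal and infant danger signs, newborn care, and family planning" while the baseline description speaks only of maternal and infant health. Table 3 lists family planning under health-related knowledge without a time point, so a mismatch of items is not shown.

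**Conclusion.** The point holds as one of precision. The outcome is not defined as endline or change for the knowledge composite, and the model leaves out a baseline score that the study plans to collect. A reader might infer bias or an invalid comparison. The documents do not support that: women are randomised, and endline, change and adjusted analyses all target the same difference between arms, provided baseline is measured before allocation.

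The gain against endline ranges from slight (1-4% of variance at r = 0.2) to material (0.44 down to 0.31 SD at r = 0.7, without clustering). The r, SD ratio, ICC and dropout are all assumptions. It concerns one of four main outcomes in an unpowered pilot, so it is an optional, low-cost improvement.

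**What to change.** First confirm that the baseline survey is completed before allocation. The protocol's Procedures and Survey data collection paragraphs do not state the order. If it is:
- In Quantitative analyses, in both documents, state that for the knowledge composite y is the endline score, and add the baseline knowledge score as a pre-specified covariate (+ beta_4 X_i).
- In the protocol's Analysis section, Aim 3, align the wording on improvements with that definition.
- Report the observed baseline-endline correlation, which is a direct input for planning the larger trial.

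The covariate need not use the same items as the composite, whereas a change score would need the same scale at both surveys. If the items differ, r and the gain are likely to be lower.

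The cost is one definition, one model term and one sentence. The term uses 1 of the 160 − 4 = 156 residual degrees of freedom and needs no new data. The drawback is that little is gained if r is low.

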Aim 2. To assess the feasibility and acceptability of the optimized *MeSSSSage* intervention. In Phase 2 we will evaluate the feasibility and acceptability of two intervention components using a controlled 4-arm factorial design (n=160; 40 per arm): 1) real-time mobile voice information and support group alone, 2) asynchronous/on-demand text-based group support only, and 3) real-time mobile voice information and support group plus asynchronous/on-demand text-based group support. Feasibility and acceptability will be assessed via back-end data, surveys, and IDIs with purposively selected participants (n=30) and moderators.

Aim 3. To explore the preliminary effectiveness of the optimized *MeSSSSage* intervention components on six-month maternal and neonatal health outcomes. Phase 2 data will help us develop a preliminary understanding of the impacts of the intervention components on MCH health-related knowledge, behaviors and outcomes including exclusive breastfeeding, immunization, family planning uptake, postnatal visits, mental health and empowerment; however, it is not statistically powered to formally assess effectiveness.

This study is significant and innovative in addressing key priorities of NICHD's Pregnancy and Perinatology Branch and using systematic, user-centered and experience-driven design approach. These results will inform the most acceptable, feasible, and potentially efficacious intervention design to be robustly tested through an R01 mechanism to assess effectiveness for maternal and infant health outcomes, explore other research questions relevant to intervention development and scale-up for postnatal health among South Asian women, and explore generalizability across populations.

Significance

[figure not shown]

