In-depth interviews (IDIs): We will recruit a subset of Phase 1 participants (n=30), equal numbers from each group, for IDIs. The interviews will explore women's experiences participating in *MeSSSSage*, the components they liked and disliked, and how to improve programming. Specifically, we will focus on timing and frequency of the group meetings, as well as feedback on the modalities tested in the different arms. We will explore their experience of the social support component of *MeSSSSage* and how this, or another, mobile technology might increase the support available to them. We will also explore which health topics related to postnatal maternal and infant health are most needed, and their main health-related concerns. IDIs will also be conducted with ASHA facilitators delivering the educational content of the mobile voice groups and moderating the mobile text groups to understand their preferences around the group components, their experiences conducting the sessions, and their perspectives on mobile provision of education, care, and support. IDIs will take place at the respondent's home, or another private location. IDIs will be transcribed and translated into English. IDI data will be coded by the research team using a grounded theory framework, using Atlas-ti text analysis software.

Phase 2: Pilot test of optimized intervention, assessment of feasibility and acceptability (Aim 2) and preliminary effectiveness on maternal and infant health outcomes (Aim 3). After analysis of Phase 1 data, we will adapt *MeSSSSage* based on participant feedback and expand content to cover topics relevant to the first 6 months postnatal. If Phase 1 data suggest the tested mobile group forum modalities are not appropriate for this population, we will adapt our study protocol to explore other feasible means to provide information and support (e.g., SMS or video). We anticipate developing and testing 2 modalities of postnatal education and support in a factorial design with a control arm for a total of 4 different group compositions. All women, including the control group, will receive the standard of care provided by the Government of India and described above. We will conduct a pilot test of the intervention using 3 groups per intervention modality (8 groups total) among 160 women (Table 2). Group structure and duration will be informed by Aim 1, but we anticipate the following:

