Table 2: *MeSSSSage* components to be tested in feasibility and acceptability assessment (Phase 2).

	Arm 1	Arm 2	Arm 3	Control
Real-time live voice call group meeting: Interactive educational program with scripted didactic component plus discussion/question. Lead and moderated by health professional.	X		X	
Text-based, asynchronous, on-demand social support: App-based small group text-based communication. Moderated by health professional.		X	X	
Standard of care: 3 visits in the first 7 days postnatal (facility and home)	X	X	X	X

Procedures: Unless found not feasible or acceptable within Phase 1 activities, women will be recruited using the approach described above (Aim 1). At the time of enrollment, the study protocol will be described to the women per informed consent procedures. Written confirmation will be obtained from interested women and their phone numbers will be collected (and tested). Women without a phone will be provided with a phone and all participants' airtime will be covered for the length of the 6-month research project. Women who consent will be randomly enrolled into 1 of the 4 study arms using a random number generator. We will test each study condition using 2 groups of women, with intervention initiation staggered 1 month apart. Women in the control group will receive the standard of care. All women will be given 50 Indian Rupees for participation in each session (in addition to airtime and phone if needed), and ASHAs will receive 150 Indian Rupees for moderating each session. Assessment of feasibility and acceptability (Aim 2) and preliminary effectiveness (Aim 3) will be accomplished using mixed-methods including quantitative surveys, in-depth interviews, and technology assessment.

Survey data collection: Baseline and endline surveys will be administered by a research assistant in the respondent's home. Endline survey will be collected roughly 6 months postnatal, after potential participation in ~24 *MeSSSSage* sessions (details to be determined during Phase 1). We will capture women's health record cards and ASHA registers to validate self-reported health outcome data. Data will be collected on a tablet using the secure REDCap mobile research administration app, stored in a password protected database at UCSF, and no identifiable information will be included with analytic datasets (identifiable data will be stored separately).

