Recruitment. Study participants will be recruited by a team consisting of an Accredited Social Health Activists (ASHA) and a research assistant, overseen by the SWACH project and principal investigators. ASHAs are familiar with the women in this study population, as they already provide information and support about health to them in the community. Primiparous women will be recruited in their last month of pregnancy during the ASHA's regular home visit. At the time of enrollment, the study protocol will be described to the women following informed consent procedures and written informed consent will be obtained from interested women. Consent will also be obtained from family members given the cultural practices in the study population. Names and contact information will be collected and stored in a password protected and encrypted computer in a locked facility.

For Aims 2 and 3 (Piloting the intervention), We will recruit for the three intervention and the one control arms using a staggered approach, recruiting one group for each arm in month one of the intervention period and one group for each arm in month two of the intervention period, to result in a total of eight groups (two per condition), for a total of 160 participants. Such a staggered approach is preferred to ensure that women are enrolled into groups with other women whose infants are similarly aged, and is feasible given the population size of our study districts.

Retention plan (i.e. Attrition reduction plan). We will carefully monitor attrition in this study.

Retention is facilitated by engagement of the ASHA, who has familiarity and experience working with the community, and previous knowledge of the participants. Contact information, including names, addresses, and phone numbers, will be collected at baseline to facilitate tracking. One of the aims of this study is to measure participation and engagement in the intervention, thus, we will be measuring retention as one of our outcomes.

PROTECTION OF HUMAN SUBJECTS

Risks to Human Subjects

Human Subjects Involvement and Characteristics of Potential Subjects

The proposed two phased project will enroll a total of (160+48) women to develop the optimal design and then understand the acceptability, feasibility, and preliminary effectiveness of the MeSSSSage intervention on maternal and infant health outcomes in India.

Inclusion criteria are:

Phase 1: 18+ years old, primiparous (pregnant with their first birth)

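### Recruitment month is a built-in design factor of Phase 2, but the SAP model omits it and allocation is not said to be drawn within month

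*SAP*

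**What the plan says.** The Recruitment and Retention Plan in the protocol sets up Phase 2 by "recruiting one group for each arm in month one of the intervention period and one group for each arm in month two", and this is meant "to result in a total of eight groups (two per condition), for a total of 160 participants". The Phase 2 Procedures agree: "We will test each study condition using 2 groups of women, with intervention initiation staggered 1 month apart". The same Procedures paragraph assigns consenting women to one of four arms with a random number generator. It mentions neither blocking nor stratification by month.

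The SAP (Quantitative analyses, repeated in the protocol under Statistical Design and Power) assesses outcomes "through fitting a series of the following linear regression model". The model has an intercept, an indicator for voice, an indicator for text, their product and one residual per participant. The Aim 3 analysis paragraph adds only "controlling for relevant socio-demographics as necessary", without naming covariates or a criterion. The Aim 2 comparisons use ANOVA for continuous outcomes and chi-square or Fisher's exact tests for categorical ones, also without month.

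The Phase 2 overview gives a group count that does not fit: "3 groups per intervention modality (8 groups total) among 160 women".

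**The concern.** A factor that the design crosses with every arm would normally appear in the analysis. Here the control arm is also filled in two monthly batches, so a shift that affects everyone (season, for example, or local service conditions) can be separated from the arm effects by one extra term. Without that term the shift is counted as unexplained variation.

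Balance of month across arms is intended but not secured. Drawing allocation without regard to month allows chance imbalance. The Phase 1 procedures, whose recruitment approach Phase 2 reuses unless Phase 1 shows it to be unworkable, also form groups by delivery date and remove some women after enrolment. If the cells end up unequal, a month difference becomes part of the arm contrasts. At stake are the precision and cleanness of the effect sizes that are to inform the larger trial.

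**Working it through.** **Inputs from the documents.** 160 women, 40 per arm, four arms; eight groups, two per condition, one per month. The plan's total reproduces both ways: 4 × 40 = 160, and 8 groups × 20 women = 160. Three groups per modality would give 3 × 3 = 9 or 3 × 4 = 12 groups, neither of which is 8, so I use two per condition. The documents give no SD, effect size, alpha or expected month difference.

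**Assumptions.** A month difference of d SD common to all arms, with d = 0, 0.2, 0.5 and 1.0; within-cell variance 1; 20 women per arm per month; 95% intervals.

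**1. Residual variance without a month term.** Each woman lies d/2 from her arm mean because of month. The extra sum of squares is 160 × (d/2)² = 40d². The SAP model has 160 − 4 = 156 residual degrees of freedom, so the expected residual variance is 1 + 40d²/156.

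**2. Half-width of a contrast between two arms.** Without month: 1.9753 × √[(2/40)(1 + 40d²/156)]. With month: 1.9754 × √(2/40) = 0.442, on 155 degrees of freedom.

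| d (assumed) | Without month | With month | Excess width |
|---|---|---|---|
| 0 | 0.442 | 0.442 | none |
| 0.2 | 0.444 | 0.442 | 0.5% |
| 0.5 | 0.456 | 0.442 | 3.2% |
| 1.0 | 0.495 | 0.442 | 12% |

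**3. Unequal cells.** Suppose one arm has 22 women in month two and 18 in month one, and another has the reverse. Their month-two shares differ by 22/40 − 18/40 = 0.10, so the contrast moves by 0.1d: 0.02 SD at d = 0.2 and 0.05 SD at d = 0.5. A month covariate removes a common shift of this kind whatever split is realised.

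**4. What the month term leaves untouched.** Women receive the intervention in groups of about 20, and the model treats them as independent. Write τ² = ICC/(1 − ICC) for the group variance. If all arms behave as groups, the model-based variance of a contrast is (2/40)(1 + 40d²/156 + 80τ²/156), while the true variance is (2/40)(1 + 20τ²). If control women are not a group, the terms become 60τ²/156 and 10τ².

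At d = 0.2 and an assumed ICC of 0.05, τ² = 0.0526. The model SE divided by the true SE is then √(1.0373/2.0526) = 0.71 with all arms grouped, and √(1.0305/1.5263) = 0.82 with an ungrouped control. At an assumed ICC of 0.01 the ratios are 0.92 and 0.96. Simulated coverage of a nominal 95% interval (6,000 runs per setting) at d = 0.2 and ICC 0.05 is 83.3% without the month term and 83.0% with it, or 89.7% and 89.3% with an ungrouped control.

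The net error turns from too wide to too narrow at an ICC of about 0.0005 (d = 0.2) or 0.003 (d = 0.5) with all arms grouped. With an ungrouped control the turning points are about 0.001 and 0.007.

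**The case against.** The best defence is that nothing depends on this. The study is an unpowered pilot, the SAP de-emphasises significance testing, neither document specifies confidence intervals, and the one numerical feasibility criterion (70% enrolment) is unaffected. Nothing in the documents points to a difference between months one month apart. In balanced cells the omission taken alone errs on the cautious side. All of this stands, and it limits the point to a small one. It does not remove the point: effect sizes by arm are planned, they feed the design of a larger trial, and the term is nearly free.

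A reader might infer that every interval from the SAP model is wider than the design warrants. The documents do not support that. With no month difference there is no widening. The same model also ignores correlation within support groups, and a very small ICC is enough to make the net intervals too narrow. Within an arm, group and month coincide, so the month term removes only the shift shared by all arms.

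A reader might also cite growing moderator experience or platform maturity as month effects. Control women have neither moderator nor platform, so these are arm-by-month effects, which an additive month term is not built to remove. Likewise, it is only an inference that the socio-demographic covariates would be picked after seeing the data; the protocol simply leaves the choice open.

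Finally, the Aim 2 chi-square and Fisher tests cannot take a covariate without becoming different tests, so the remedy should not extend to them.

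**Conclusion.** The point holds in a modest form. Recruitment month is a structural factor crossed with all four arms; the SAP model leaves it out, and the protocol does not secure its balance through allocation within month. In balanced cells the loss is about 0.5% of the half-width at an assumed 0.2 SD month difference, 3.2% at 0.5 SD and nothing at zero. The arm contrasts carry no bias while the cells are equal; otherwise they move by the difference in month shares times the month difference, which is 0.1d in the example. These sizes rest on assumed month differences and on two groups of 20 per arm.

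This is a cheap improvement in a pilot, not a flaw that undermines it. No statement about the overall width of the intervals follows, because unmodelled group correlation pulls the other way and may be larger.

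**What to change.** - **Allocation:** state in the Phase 2 Procedures that the random allocation is drawn separately within each recruitment month.
- **SAP regression:** add recruitment month (1 or 2, as recorded at allocation) as a prespecified fixed covariate for all outcomes and all four arms.
- **Aim 2:** add month to the ANOVA for continuous outcomes; leave the chi-square and Fisher tests as they are.
- **Socio-demographics:** make the month-adjusted model the main analysis, and present any socio-demographic adjustment as sensitivity, in place of the open-ended wording under Aim 3.
- **Limit to state:** say that the month term does not account for correlation within support groups, which must be handled separately.
- **Group count:** reconcile the Phase 2 overview with the two groups per condition given elsewhere.

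The cost is one of 156 residual degrees of freedom in the regression, an allocation list split by month, and a few sentences of text.
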